### 15.3 DERIVED EFFICACY AND SAFETY VARIABLES

The efficacy variables are derived as follows:

- MADRS total score is the sum of the 10 items from the MADRS. If more than 2 items of the MADRS are missing, then the total score will be set to missing
- *Responder* is defined as a patient with  $\geq 50\%$  reduction from Day 0 MADRS total score
- *Remitter* in the randomized treatment period is defined as a patient with MADRS total score  $\leq 10$

For the MADRS [REDACTED], the total score at a particular visit will be calculated using  $(\text{sum of nonmissing items}) \times (\text{total number of items}) / (\text{number of nonmissing items})$  only if the number of missing items is less than the specified number for each variable. Otherwise, the total score will be set to missing.

The primary efficacy parameter was defined in section 8.1. A relapse will be defined programmatically as meeting any of the following criteria:

- An observed MADRS total score  $\geq 18$  for two consecutive assessments as determined from the MADRS data (not the Relapse CRF). The 2 MADRS assessments must occur on different calendar dates.
- An observed increase in CGI-S score  $\geq 2$  compared with that obtained at randomization as determined from the CGI-S data (not the Relapse CRF).

- Marked as a relapse on the Relapse CRF with the primary reason for relapse indicating “Risk of Suicide”.
- Marked as a relapse on the Relapse CRF with the primary reason for relapse indicating “Need for hospitalization due to worsening of depression”.
- Marked as a relapse on the Relapse CRF with the primary reason for relapse indicating “Need for alternative treatment for depressive symptoms”.

The first relapse date for a patient is defined as the earliest assessment date in which any of the relapse criteria mentioned above were met, obtained either from the date recorded on the Relapse CRF (for the primary reasons of “Risk of Suicide”, “Need for hospitalization due to worsening of depression” or “Need for alternative treatment for depressive symptoms”) or the dates of the corresponding MADRS or CGI-S assessments. For the relapses based on MADRS total score  $\geq 18$  at 2 consecutive visits, the relapse date is defined as the assessment date of the first visit of the 2 consecutive assessments.

#### **15.4 REPEATED OR UNSCHEDULED ASSESSMENTS OF SAFETY PARAMETERS**

If end-of-study assessments are repeated or if unscheduled visits occur, the last nonmissing postbaseline assessment will be used as the end-of-study assessment for generating summary statistics. However, all postbaseline assessments will be used for PCS value determinations, and all assessments will be presented in the data listings.

#### **15.5 MISSING SEVERITY ASSESSMENT FOR ADVERSE EVENTS**

If severity is missing for an AE that started before the date of the first dose of open-label IP, an intensity of mild will be assigned. If severity is missing for an AE that started on or after the date of the first dose of open-label IP, a severity of severe will be assigned. The imputed values for severity assessment will be used for the incidence summary; the values will be shown as missing in the data listings.

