## 9.1 ADVERSE EVENTS

AEs will be coded using the *Medical Dictionary for Regulatory Activities*.

An AE (classified by preferred term) that occurs during the OLTP or thereafter will be considered a treatment-emergent adverse event (TEAE) if it was not present before the date of the first dose of IP in the lead-in study or was present before the first dose of IP in the lead-in study and increased in severity during the OLTP or thereafter. An AE that becomes serious during the OLTP or thereafter will also be considered as a TEAE. If more than 1 AE is reported before the date of the first dose of IP in the lead-in study and coded to the same preferred term, the AE with the greatest severity will be used as the benchmark for comparison with the AEs occurring during the OLTP or thereafter that were also coded to that preferred term. An AE that occurs more than 30 days after the date of the last dose of IP will not be counted as a TEAE.

An AE (classified by preferred term) that occurs during the OLTP of the study will be considered a newly emergent adverse event (NEAE) if the AE was not present before the first dose of IP in the OLTP or it was present before the first dose of IP in the OLTP and increased in severity during the OLTP. An AE that becomes serious during the OLTP will also be considered as an NEAE. If more than 1 AE is reported before the first dose of IP in the OLTP and coded to the same preferred term, the AE with the greatest severity will be used as the benchmark for comparison with the AEs occurring during the OLTP that were also coded to that preferred term.

An AE (classified by preferred term) that occurs during the DBTP of the study will be considered an NEAE if the AE was not present before the first dose of IP in the DBTP or it was present before the first dose of IP in the DBTP and increased in severity during the DBTP. An AE that becomes serious during the DBTP will also be considered as an NEAE. If more than 1 AE is reported before the first dose of IP in the DBTP and coded to the same preferred term, the AE with the greatest severity will be used as the benchmark for comparison with the AEs occurring during the DBTP that were also coded to that preferred term.

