An AE (classified by preferred term) that occurs during the SFU of the study will be considered an NEAE if the AE was not present before or at Visit 122 or it was present before or at Visit 122 and increased in severity during the SFU. An AE that becomes serious during the SFU will also be considered as an NEAE. If more than 1 AE is reported before or at Visit 122 and coded to the same preferred term, the AE with the greatest severity will be used as the benchmark for comparison with the AEs occurring during the SFU that were also coded to that preferred term.

An AE that occurs more than 30 days after the date of the last dose of IP will not be counted as an NEAE.

The number and percentage of patients reporting TEAEs and NEAEs during the OLTP will be tabulated overall by SOC and preferred term. The number and percentage of patients in each treatment group reporting TEAEs and NEAEs during the DBTP and during the SFU will be tabulated by SOC and preferred term; by SOC, preferred term, and severity; and by SOC, preferred term, and causal relationship to the IP. If more than 1 AE is coded to the same preferred term for the same patient during the same treatment period, the patient will be counted only once for that preferred term using the most severe and most related occurrence for the summarization by severity and by causal relationship to the IP.

[figure not shown]
The incidence of common ( $\geq 2\%$  of patients in any treatment group) TEAEs and NEAEs during the OLTP will be summarized overall by preferred term. Similarly, the incidence of common TEAEs and NEAEs during the DBTP and during the SFU will be summarized by preferred term and treatment group and will be sorted by decreasing frequency starting with the weekly rapastinel group followed by the biweekly rapastinel group.

[figure not shown]
An SAE that occurred between the date of the first dose of IP in the OLTP and 30 days after the date of the last dose of IP, inclusive, will be considered a treatment-emergent SAE (TESAE). The number and percentage of patients who had TESAEs during the OLTP will be summarized overall by preferred term and sorted by decreasing frequency. The number and percentage of patients who had TESAEs during the DBTP and during the SFU will be summarized by treatment group and preferred term and will be sorted by decreasing frequency starting with the weekly rapastinel group followed by the biweekly rapastinel group.

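### A missing AE severity is imputed as severe from the first open-label dose onward, and as the natural reading makes that value the benchmark for the next period, newly emergent AEs in the DBTP and SFU are under-counted

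*SAP*

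**What the plan says.** Section 15.5 has two imputation rules, separated by one date. A missing severity on an AE that started "before the date of the first dose of open-label IP, an intensity of mild will be assigned". On an AE that started on or "after the date of the first dose of open-label IP, a severity of severe will be assigned". On use, the section says: "The imputed values for severity assessment will be used for the incidence summary". Listings continue to show the value as missing.

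Section 9.1 defines NEAEs separately for each period. In the DBTP, an AE qualifies if its preferred term was not there before double-blind dosing, or if "it was present before the first dose of IP in the DBTP and increased in severity during the DBTP". Where several earlier AEs share the term, "the AE with the greatest severity will be used as the benchmark for comparison with the AEs occurring during the DBTP". Seriousness is a separate route: "An AE that becomes serious during the DBTP will also be considered as an NEAE". The SFU definition has the same structure, with AEs up to and including Visit 122 as the earlier set; there "the AE with the greatest severity will be used as the benchmark for comparison with the AEs occurring during the SFU".

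The output is comparative: "The number and percentage of patients in each treatment group reporting TEAEs and NEAEs during the DBTP and during the SFU will be tabulated", by system organ class and preferred term, and also split by severity and by causality.

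**The concern.** The imputation has one cut-off date, and the NEAE definitions have three reference points. At the first open-label dose they coincide: earlier AEs of unknown severity get a low benchmark and later ones a high grade, so both choices favour counting an event. At the first double-blind dose they do not coincide. The open-label period is then the earlier period, yet its missing severities are set to the highest named grade. The same happens at Visit 122 for AEs that began in either treatment period.

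NEAEs are the severity-benchmarked AE display anchored at the first double-blind dose. Every randomised patient has already received open-label rapastinel, so this display shows what is new or worse since that dose. A rule that turns an unknown earlier grade into an unbeatable benchmark lowers the counts in it.

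**Working it through.** The SAP states no figure on this point, so there is none to reproduce. The check applies the rules to every possible case.

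**Inputs**
- Imputed grade for an open-label AE with missing severity: severe (Section 15.5).
- Imputed grade for a double-blind AE with missing severity: severe (same rule).
- Benchmark: the highest severity among earlier AEs of the preferred term (Section 9.1).
- Grades, assumed: mild (1) < moderate (2) < severe (3). The visible SAP names only mild and severe.

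**Rule for a term already present:** NEAE if the AE is serious, or if its DBTP grade > benchmark grade.

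**Benchmark as written.** The missing open-label severity becomes 3. If other open-label AEs of the term have known grades, the maximum is still 3.

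**Alternative.** The missing severity becomes 1 because the AE started before the first double-blind dose.

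| Non-serious DBTP AE, same term | Grade | Benchmark 3 (as written) | Benchmark 1 (mild) |
|---|---|---|---|
| mild | 1 | 1 > 3: no | 1 > 1: no |
| moderate | 2 | 2 > 3: no | 2 > 1: yes |
| severe | 3 | 3 > 3: no | 3 > 1: yes |
| missing, imputed severe | 3 | 3 > 3: no | 3 > 1: yes |
| **Counted as NEAE** | | **0 of 4** | **3 of 4** |

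A serious DBTP AE counts in 4 of 4 cases under either benchmark. The SFU comparison works the same way, with an open-label or double-blind AE of missing severity as the benchmark. The mild column assumes that no other earlier AE of the term has a higher known grade.

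**Does the imputed value reach the benchmark?** Section 15.5 sends imputed values to the incidence summary, and the NEAE tables are incidence summaries. In addition, the visible Section 9.1 tabulates AEs only for the OLTP, DBTP and SFU. AEs that began before the first open-label dose are not tabulated as such, so the mild rule for them has little visible purpose except as a benchmark. Similarly, the visible text plans no severity breakdown for the OLTP, so a severity table is not the evident use of an imputed open-label grade.

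**TEAE tables.** Their benchmark is set before the first dose in the lead-in study. That date is before the first open-label dose, so a missing severity there is mild. An open-label AE with missing severity cannot remove a double-blind TEAE.

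**The case against.** The strongest objection is that the link is inferred. Section 15.5 does not say that imputed severities set NEAE status, and the benchmark text in Section 9.1 does not mention imputed values. The imputation might be meant only for tables split by severity, and parts of the surrounding text are redacted. This stands as a limit on certainty. It does not remove the problem: on that reading the visible SAP has no rule for comparing an AE with a benchmark of unknown grade, and a clarifying sentence is still needed.

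Four stronger inferences are tempting, and the document does not support them.

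- **That worsening events drop out of the randomised safety comparison, or that NEAEs are its only useful AE measure.** DBTP TEAEs are tabulated by arm beside NEAEs, including by severity and causality. Serious AEs and AEs leading to discontinuation are also summarised by arm. An affected event is absent from one of two parallel displays.
- **That the suppressed events are true worsening.** The earlier grade is unknown. If it was really severe, a mild benchmark would flag a moderate, improved recurrence as newly emergent.
- **That the arms are biased against each other.** For the DBTP tables the benchmark AE began while all patients were on the same open-label regimen, and nothing suggests that missingness would differ by later arm. For the SFU the benchmark AE can begin after randomisation, so that reassurance is weaker, but no difference is shown there either.
- **That the rule defeats its own stated aim.** Section 15.5 gives no rationale. One can say only that its effect at the first open-label dose differs from its effect at later reference points.

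**Conclusion.** The concern holds in a limited form. On the natural reading, a missing severity in an earlier period becomes a severe benchmark, and every later non-serious AE of that term is excluded from the NEAE counts for the DBTP or SFU. The effect on those counts is always downward.

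Its overall size cannot be computed, because the SAP gives no rate of missing severity. It requires a missing severity in an earlier period together with a later non-serious AE of the same preferred term in the same patient, which is probably rare. The 0-of-4 result applies only within that subset.

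The conclusion rests on two assumptions: that imputed values enter NEAE derivation, and that severe is the top grade. The efficacy analyses and the TEAE tables are unaffected. This is a small defect in a stated rule, and worth correcting because the correction is cheap.

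**What to change.** Add one sentence to Section 15.5: for deriving NEAE status, a missing severity is set to mild for any AE that started before the reference point of the period being tabulated. The reference points are the first open-label dose for the OLTP, the first double-blind dose for the DBTP, and Visit 122 (inclusive, to match Section 9.1) for the SFU. Keep severe for severity summaries in the period where the AE began. This extends the existing mild rule to each period's own baseline and settles whether imputed values enter the derivation.

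The cost is one sentence and one derivation line. Slightly more NEAEs will be reported, and some will not be true worsening. One record may also carry two imputed grades, mild as a benchmark and severe for display. The sentence should therefore make clear that an AE continuing across a reference point is not compared with itself and flagged only because its two imputed grades differ.

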#### **15.6 MISSING CAUSAL RELATIONSHIP TO INVESTIGATIONAL PRODUCT FOR ADVERSE EVENTS**

If the causal relationship to the IP is missing for an AE that started on or after the date of the first dose of open-label IP, a causality of yes will be assigned. The imputed values for causal relationship to randomized treatment will be used for the incidence summary; the values will be shown as missing in the data listings.

#### **15.7 MISSING DATE INFORMATION FOR ADVERSE EVENTS**

The following imputation rules only apply to cases in which the start date for an AE is incomplete (ie, partly missing).

### **Missing month and day**

- If the year of the incomplete start date is the same as the year of the first dose of open-label IP, the month and day of the first dose of open-label IP will be assigned to the missing fields.
- If the year of the incomplete start date is before the year of the first dose of open-label IP, *31 Dec* will be assigned to the missing fields.
- If the year of the incomplete start date is after the year of the first dose of open-label IP, *01 Jan* will be assigned to the missing fields.

### **Missing month only**

- If only the month is missing, the day will be treated as missing and both the month and the day will be replaced according to the above procedure.

### **Missing day only**

- If the month and year of the incomplete start date are the same as the month and year of the first dose of open-label IP, the day of the first dose of open-label IP will be assigned to the missing day.
- If either the year of the incomplete start date is before the year of the date of the first dose of open-label IP or if both years are the same, but the month of the incomplete start date is before the month of the date of the first dose of open-label IP, the last day of the month will be assigned to the missing day.
- If either the year of the incomplete start date is after the year of the date of the first dose of open-label IP or if both years are the same, but the month of the incomplete start date is after the month of the date of the first dose of open-label IP, the first day of the month will be assigned to the missing day.

If the stop date is complete and the imputed start date as above is after the stop date, the start date will be imputed by the stop date.

If the start date is completely missing and the stop date is complete, the following algorithm will be used to impute the start date:

- If the stop date is after the date of the first dose of open-label IP, the date of the first dose of open-label IP will be assigned to the missing start date.
- If the stop date is before the date of the first dose of open-label IP, the stop date will be assigned to the missing start date.

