## 15.8 MISSING DATE INFORMATION FOR PRIOR OR CONCOMITANT MEDICATIONS

For prior or concomitant medications, including background ADT, incomplete (ie, partially missing) start dates and/or stop dates will be imputed. When the start date and the stop date are both incomplete for a patient, the start date will be imputed first.

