### 15.8.1 Incomplete Start Date

The following rules will be applied to impute the missing numeric fields for an incomplete prior or concomitant medication start date. If the stop date is complete (or imputed) and the imputed start date is after the stop date, the start date will be imputed using the stop date.

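### Section 15.7 tests an imputed AE start date against the stop date only when the stop date is complete, so an AE with a recorded stop month before open-label dosing can be given an open-label start

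*SAP*

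**What the plan says.** Section 15.7 opens by limiting its scope to start dates: "The following imputation rules only apply to cases in which the start date for an AE is incomplete". The readable text has no rule that imputes or uses a partial AE stop date.

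Where month and day are missing and the year equals that of the first open-label dose, "the month and day of the first dose of open-label IP will be assigned to the missing fields". A start that lacks only the month follows the same route: "If only the month is missing, the day will be treated as missing".

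One sentence guards against a start later than the stop. It is conditional: "If the stop date is complete and the imputed start date as above is after the stop date", the start is replaced by the stop date. A separate two-bullet algorithm covers a start with no date information, and it too requires a complete stop: "If the start date is completely missing and the stop date is complete".

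Section 2.0 starts the OLTP at the first open-label dose. Section 9.1 counts an AE occurring in the OLTP or later as a TEAE "if it was not present before the date of the first dose of IP in the lead-in study", or if it worsened or became serious. The OLTP NEAE definition has the same form, with the first OLTP dose as its reference.

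**The concern.** Assigning an AE of uncertain onset to treatment is ordinary conservative practice when onset on treatment is possible. Here it is not possible: a stop recorded in a month before the first open-label dose rules out open-label onset whatever the missing day is. The plan accepts this reasoning when the day is recorded, because it then moves the start back to the stop date. Without the day, the same AE receives a start later than its recorded stop month.

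At stake are the OLTP TEAE and NEAE counts, which can include events that ended before open-label dosing, and listings in which an AE begins after it stopped.

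**Working it through.** The plan gives no figure to reproduce. The check applies the Section 15.7 rules to dates.

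**Example.** Assumed, not from the SAP: first open-label dose 10 Jun 2018; AE start recorded as 2018 only.

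1. The start year equals the dose year, so the start is set to 10 Jun 2018.
2. Stop recorded as 20 Mar 2018: the stop is complete and 10 Jun is later, so the start becomes 20 Mar 2018. The check works.
3. Stop recorded as Mar 2018, day missing: the condition is not met, so the start stays at 10 Jun 2018.
4. The latest possible stop in step 3 is 31 Mar 2018. The gap is 30 (April) + 31 (May) + 10 (June) = 71 days.
5. 10 Jun 2018 is the first day of the OLTP, so an AE dated by its imputed start falls inside it.

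**Which branches are affected.** The rules were applied with the first dose on the 10th of each month of 2018 in turn. Stops were known to the month only, earlier than the dose month and compatible with the start information.

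| Start information | Combinations | Open-label start under the SAP |
|---|---|---|
| Dose year, month and day missing | 66 | 66 |
| Dose year, day missing | 286 | 0 |
| Earlier year, day missing | 1728 | 0 |
| Earlier year, month and day missing | 210 | 0 |

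The 66 is a count of calendar combinations: a dose in month k leaves k − 1 earlier stop months, and 0 + 1 + … + 11 = 66. The other branches are safe because a known earlier start month puts the start on the last day of that month, and an earlier start year puts it no later than 31 Dec of that year. Both precede the dose.

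**With the limit extended** to the last day of a recorded stop month, the start in step 3 becomes 31 Mar 2018, and 0 of the 66 combinations have an open-label start.

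**Start completely missing, stop partial.** No start is assigned, because the algorithm needs a complete stop. This is an undefined case and does not produce an open-label start.

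**The case against.** The case for leaving the text alone has several parts.

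- **The rule is conservative by design.** Sections 15.5 and 15.6 likewise treat a missing severity as severe and a missing causality as related. That supports assigning uncertain AEs to treatment. It does not support assigning one whose recorded stop month excludes open-label onset.
- **Classification need not follow the imputed start.** Section 9.1 asks whether the AE was present before the reference dose and does not say that presence is judged from the imputed start alone. A programmer could use the stop month as evidence of earlier presence. This stands, and it is why the AE can be miscounted rather than must be.
- **Some rules may not be readable.** Section numbering passes from 15.8 to 15.10. A rule in the missing part cannot be excluded.

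Stronger readings are tempting, and the SAP does not support them:

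- **That Section 15.7 contradicts Section 15.8.** For medications, "incomplete (ie, partially missing) start dates and/or stop dates will be imputed", and the check runs "If the stop date is complete (or imputed) and the imputed start date is after the stop date". But Section 15.8 imputes the start first when both dates are incomplete, and Section 15.8.2 then moves an earlier imputed stop up to the start. A medication with the example's dates would also start on 10 Jun 2018. Section 15.8 is neither a contradiction nor a model for the fix.
- **That the by-arm tables of the double-blind treatment period (DBTP) are biased.** A DBTP TEAE count would change only if the AE had ended before the lead-in dose, dropped out of the Section 9.1 severity benchmark because presence was judged from the imputed start alone, and recurred under the same preferred term without being more severe or becoming serious. DBTP NEAE counts are not inflated this way, since an AE placed in the OLTP still counts as present before the first double-blind dose. The dates at issue precede randomization, so nothing evident favours an arm.
- **That 66 of 66 is a frequency.** It shows only that the branch always fails, not how often it occurs.

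**Conclusion.** The concern holds in a narrow form. Three conditions must coincide: the AE start lacks the month (or month and day), its year is that of the first open-label dose, and the stop is recorded to a month before that dose but without a day. Under the readable text, every such AE receives the first open-label dose date as its start. It can then enter the OLTP TEAE and NEAE counts if classification follows the imputed start.

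The SAP gives no basis for a count, and the number is probably small. The effect is mainly on OLTP tables, which are tabulated overall and not by arm. No between-arm bias is shown and the efficacy analysis is untouched. This is a minor correction, worth making because the rule overrides information already in the record.

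**What to change.** Replace the conditional sentence in Section 15.7 with: *If the imputed start date is later than the latest calendar date consistent with the recorded stop date (the stop date if complete; the last day of the recorded month if only the day is missing), the start date is set to that latest date.*

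For a completely missing start with a partial stop, run the existing two-bullet algorithm at the end of Section 15.7 using that same latest possible stop date. A limit alone would not help there, because no start has been assigned.

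AEs whose partial stop is compatible with open-label onset keep the present conservative assignment. The cost is a short change of wording and a small change to the date derivation, with no new data. The downside is that a few OLTP TEAE and NEAE counts may become slightly lower.
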